5.1.1 Informed Consent

Study site personnel must explain to potential study participants or parents/guardians of potential study participants all aspects of the study, including all scheduled visits and activities. Study site personnel must obtain signed informed consent and assent (where required) before any study-specific procedures are conducted unless the procedures are part of routine standard of care. The informed consent process must be documented in the subject's source documents ([Section 13.1.3](#)).

5.1.2 Subject Identification Numbers

After obtaining signed informed consent and assent (where required), study site personnel will access the interactive response system to assign a subject ID number for each potential study participant. This unique number will be used to identify the subject for the remainder of the study.

For subjects with written informed consent and assent (where required) who subsequently do not meet eligibility criteria or if consent is withdrawn, study site personnel will document the screen failure or consent withdrawal in the subject's source documents. The documentation will include demographics and medical history, the reason for screen failure, and procedures performed.

5.1.3 Screening Procedures

Screening procedures are listed in [Appendix 4](#). All screening procedures must be completed within 42 days after signed informed consent and assent (where required) are obtained.

The investigator or designee will assess the eligibility of each subject. All screening procedure results and relevant medical, allergy, and food allergen exposure history must be available before eligibility can be determined. All inclusion criteria must be met and none of the exclusion criteria may apply. No eligibility waivers will be granted.

Rescreening may be considered in certain circumstances on a case-by-case basis following discussion with the medical monitor.

5.2 Treatment Periods

5.2.1 Treatment Period Visit Windows

All up-dosing and maintenance study site visits have a visit window of ± 3 days (ie, 3 days before or after the expected visit day). The initial dose-escalation day 1 visit must begin within 42 days after obtaining signed consent/assent and within 10 days after the second day of the screening DBPCFC. If circumstances create a safety risk (eg, an intercurrent illness), day 1 may be delayed after discussion with the medical monitor.

Day 2 should be the next consecutive day after day 1. If circumstances create a safety risk (eg, an intercurrent illness), day 2 may be delayed after discussion with the medical monitor.

Study treatment will continue daily during visit windows. Study product supplies must be considered when scheduling visits.

5.2.2 Randomization Procedures

After confirmation of eligibility, study site personnel will access the interactive response system to assign subjects to randomized study treatment (AR201 or placebo), which is to begin within 42 days after signed consent/assent and should be the same day as randomization. Randomized study treatment may start within 3 days after randomization only if starting the same day is not feasible (eg, for certain unexpected circumstances that may create a safety risk, such as intercurrent illness). A longer window may be allowed on a case-by-case basis following approval from the medical monitor.

5.2.3 General Study Visit Procedures

Day 1 will be the first day of randomized study treatment (AR201 or placebo). Study procedures will be performed at each visit according to the schedule of activities ([Appendix 5](#)).

Before administration of the first and any subsequent dose of study product at the study site, the subject's health status must be at baseline state, including no active wheezing, flare of atopic disease (eg, atopic dermatitis), or suspected intercurrent illness. The subject must have fully recovered from any previous illness for at least 3 days, depending on the severity of the illness per investigator assessment.

A study physician must always be readily available during dosing at the study site. Subjects will be evaluated for signs and symptoms of an allergic reaction at 15 to 30 minutes postdose and approximately every 30 minutes thereafter (with measurements of blood pressure and heart rate), until at least 90 minutes postdose or the end of the observation period ([Section 8.7.1](#)), whichever is last.

Allergy symptoms will be assessed as follows:

- Symptoms of allergic reactions will be evaluated per [Section 8.7.1](#).
- The tolerability of study product will be evaluated per [Section 8.7.1.1](#).
- The treatment of allergic reactions and dose adjustment of study product will follow guidelines per [Section 8.7.2](#) and [Section 8.7.3](#).

On the day after each study site visit, site staff will contact the subject or parent/caregiver by telephone to perform the following ([Appendix 5](#)):

- Inquire if any adverse events occurred (including allergy symptoms, GI symptoms, and exposure to food allergen).
- Provide guidance in managing adverse events.
- Remind the subject or parent/caregiver to record the subject's symptoms in the study diary.

- Inquire about compliance with study product dosing.

5.2.3.1 Initial Dose-Escalation Procedures

Initial dose-escalation procedures are listed in [Appendix 5](#). Subjects may have clear liquids or flavored gelatin during the dosing procedures.

Day 1

Subjects will be required to discontinue antihistamines and other medications that could interfere with the assessment of an allergic reaction for 5 half-lives of the medication before the first day of dose escalation.

Study product will be administered in 5 increasing doses in a stepwise manner in 20- to 30-minute intervals as tolerated. The 5 doses and cumulative dose of study product to be consumed on day 1 are shown in [Table 1](#).

Table 1: Study Product Single Doses and Cumulative Dose on Day 1

Dose Number	Study Product Dose (mg)	Cumulative Dose (mg)
1	0.2	0.2
2	0.4	0.6
3	0.8	1.4
4	1	2.4
5	2	4.4

The time points for study product dosing and assessments of blood pressure, heart rate, temperature, and allergic reaction are provided in [Table 2](#). Subjects who develop dose-limiting or moderate allergy symptoms at ≤ 1 mg doses of study product, severe symptoms at any dose, or use rescue medications (except ≤ 2 doses of antihistamines, [Section 8.7.3.1](#)) at ≤ 1 mg doses of study product or for severe symptoms at the 2 mg dose will stop dose escalation and discontinue early from the study ([Section 5.3](#)).

Table 2: Initial Dose-Escalation Day 1 Procedures

Study Product Dose (Timing) Time Point	Administer Study Product	Blood Pressure	Heart Rate	Temp	Assess Allergy Symptoms
Predose		X	X	X	
0.2 mg	X				
15-30 min postdose		X	X		X
0.4 mg (20-30 min after previous dose) [1]	X				
15-30 min postdose		X	X		X
0.8 mg (20-30 min after previous dose) [1]	X				
15-30 min postdose		X	X		X
1.0 mg (20-30 min after previous dose) [1]	X				
15-30 min postdose		X	X		X
2 mg (20-30 min after previous dose) [1]	X				
15-30 min postdose		X	X		X
Approximately every 30 min until at least 90 min after last dose or end of observation per allergy symptoms [2]		X	X		X

[1] If the previous dose was tolerated ([Section 8.7.1.1](#)). If the subject has dose-limiting or moderate allergy symptoms anytime at ≤ 1 mg, severe symptoms at any dose, or requires rescue medications (except ≤ 2 doses of antihistamines, [Section 8.7.3.1](#)) at ≤ 1 mg or for severe symptoms at 2 mg, stop dose escalation and discontinue the subject early from the study. If 1 mg is tolerated or no more than mild or moderate symptoms occur at 2 mg, the subject will return for a single 1 mg dose on day 2.

[2] The length of observation is based on signs/symptoms of allergic reaction per [Section 8.7.1](#).

Min, minutes; temp, temperature.

Day 2

Subjects who tolerate at least 1 mg study product and have no more than mild or moderate allergy symptoms at the 2 mg dose on day 1 will return to the study site on day 2 to receive a single 1 mg dose under medical supervision. Day 2 should be the next consecutive day after day 1. If circumstances create a safety risk (eg, an intercurrent illness), day 2 may be delayed after discussion with the medical monitor. Subjects who tolerate the 1 mg dose with no more than mild symptoms that are not dose-limiting will receive an adequate supply of study product to continue daily dosing at home at 1 mg/day during up-dosing ([Section 5.2.3.2](#)).

Subjects who develop moderate or severe symptoms after consuming the 1 mg dose on day 2, or use rescue medications (except ≤ 2 doses of antihistamines, [Section 8.7.3.1](#)), will stop study product dosing and discontinue early from the study ([Section 5.3](#)).

5.2.3.2 Up-Dosing Procedures

Up-dosing procedures are listed in the schedule of activities in [Appendix 5](#). Additional procedures will be performed at the 80 mg and 300 mg up-dosing visits ([Appendix 5](#)).

Up-dosing study site visits are every 2 weeks for approximately 6 months (minimum 22 weeks if up-dosing proceeds without holding or reducing a dose level; maximum 40 weeks).

Up-dosing will begin when subjects begin daily dosing with study product at 1 mg/day at home for 2 weeks. Subjects who tolerate 1 mg/day for 2 weeks will return to the study site to receive a 3 mg dose. Subjects who tolerate the 3 mg dose at the study site will receive study product to continue daily dosing at home with 3 mg/day for a total of 2 weeks. AR201 dose escalations will continue in this manner up to 300 mg/day as shown in [Table 3](#). Dose adjustments may be allowed ([Section 8.7.3.2](#), [Section 8.7.4](#)).

Subjects who reach the 300 mg/day dose within 40 weeks and tolerate the first 300 mg dose with no more than mild allergy symptoms that are not dose-limiting will begin maintenance treatment ([Section 5.2.3.3](#)). Subjects who do not reach the 300 mg/day dose within 40 weeks of day 1 will discontinue early from the study ([Section 5.3](#)).

Table 3: Up-Dosing Dose-Escalation Schedule (1-300 mg)

Dose Number	Study Product Dose (mg)	Interval (weeks)	Increase From Previous Repeated Dose
1	1	2	Not applicable
2	3	2	200%
3	6	2	100%
4	12	2	100%
5	20	2	67%
6	40	2	100%
7	80	2	100%
8	120	2	50%
9	160	2	33%
10	200	2	25%
11	240	2	20%
12	300	-	25%

Up-dosing begins with the first 1 mg/day dose of study product at home.

5.2.3.3 Maintenance Procedures

The maintenance procedures are listed in [Appendix 5](#). Maintenance visits will occur every 4 weeks for approximately 12 weeks. Dose adjustments may be allowed ([Section 8.7.3.2](#), [Section 8.7.4](#)). The maintenance period may be extended by up to an additional 4 weeks to

accommodate dose adjustments during the last 2 weeks of maintenance. Study product will be administered under medical supervision at the study site during maintenance visits; subsequent maintenance doses will be administered daily at home as tolerated.

An exit DBPCFC will be performed at the end of maintenance, followed by an open baked whole egg food challenge within 14 days after the second day of the exit DBPCFC ([Section 9.1.1](#), [Section 9.1.2](#), [Appendix 1](#), [Appendix 2](#), [Appendix 5](#)). The 300 mg daily dose of study product must be tolerated for approximately 2 consecutive weeks before having the exit DBPCFC. In exceptional circumstances when the 300 mg daily dose is not taken for approximately 2 consecutive weeks before the planned exit DBPCFC for reasons unrelated to the study product, the medical monitor should be contacted to determine whether the exit DBPCFC is to be attempted. Discussion with the medical monitor is required to determine whether the exit DBPCFC and/or open baked whole egg food challenge may be attempted if the food challenge is delayed due to circumstances that create a safety risk (eg, an intercurrent illness).

5.2.4 Unscheduled Visit Procedures

Unscheduled visit procedures are listed in the schedule of activities. Other study procedures may be performed as clinically appropriate.

Unscheduled visits may be performed anytime to assess or follow up adverse events, or at the request of the subject or investigator. The date and reason for the unscheduled visit must be recorded in the source documentation.

5.3 Early Discontinuation

Early treatment discontinuation is defined as *permanent* cessation of study product administration anytime before completing approximately 9 months of overall treatment (initial dose escalation, up-dosing, and maintenance), including at least 4 weeks at 300 mg/day. Subjects who discontinue early will have early discontinuation procedures approximately 14 days after their last dose of study product according to the schedule of activities ([Appendix 5](#)). For a subject who discontinues early from the study, study treatment assignment will be unblinded after the study is completed.

Subjects with unresolved adverse events at early discontinuation or who had GI adverse events of interest ([Section 8.7.6.2.1](#)) will have safety follow-up per [Section 5.5](#).

Temporary treatment interruption (eg, due to an adverse event) will not be considered early discontinuation.

The primary reasons for early discontinuation of study product are listed in [Table 4](#).

Table 4: Primary Reasons for Early Discontinuation

Category Reason	Comment
Protocol/ Investigator-Initiated	
Adverse event or intercurrent illness	
Subjects must discontinue early for any intolerable adverse event that may lead to undue risk if study treatment were continued, such as the following:
 
 • Life-threatening symptoms, including anaphylaxis resulting in hypotension, neurologic compromise, or mechanical ventilation related to study treatment or food challenge. • Severe dose-related symptoms that require intensive therapy (per investigator assessment, but may include interventions such as IV epinephrine, intubation, or admission to an intensive care unit) or are recurrent. 
Subjects must discontinue early for any adverse event that meets the early discontinuation criteria for study product tolerability or delays as follows:
 
 • Tolerability of study product: 
 – Dose-limiting or moderate symptoms at ≤ 1 mg or severe symptoms at any dose on initial dose-escalation day 1; dose-limiting, moderate, or severe symptoms on initial dose-escalation day 2 – Unable to reach the 300 mg/day dose within 40 weeks of up-dosing • Use of rescue medications: 
 – Treatment with epinephrine, beta-agonist, oxygen, IV fluids, > 2 doses of antihistamines, and/or glucocorticosteroids at ≤ 1 mg study product or for severe symptoms at the 2 mg dose on initial dose-escalation day 1 or 2 – Treatment with 3 or more doses of epinephrine for an event of dose-related symptoms anytime • Dose adjustment of study product: 
 – Unable to escalate the dose level after 3 consecutive failed attempts with at least 2 weeks between each escalation attempt – Unable to tolerate 3 attempts at dose reduction after mild or moderate symptoms, or unable to tolerate 1 attempt at dose reduction after severe symptoms • Missed ≥ 15 consecutive days of study product dosing due to any circumstances (eg, as part of the treatment for an intercurrent adverse event). Missed doses per dose adjustment guidelines in Section 8.7.3.2 are allowed. 
Subjects must discontinue early for any intolerable adverse event that cannot be ameliorated using adequate medical intervention or that in the opinion of the investigator or sponsor may lead to undue risk if study treatment were continued, such as the following:
 
 • Poor control or persistent activation of secondary atopic disease (eg, atopic dermatitis, asthma). • Development of biopsy-documented eosinophilic esophagitis.

Category Reason	Comment
Use of prohibited medication	Prohibited concomitant medications are listed in Section 7.4 .
Pregnancy	Pregnancy will be followed to delivery or until termination of the pregnancy (Section 8.7.7.2).
Death	
Investigator decision	Investigators may elect to discontinue a subject's study treatment if they decide it is in the subject's best interest. Select this category if adverse events/intercurrent illness, use of prohibited concomitant therapy, pregnancy, death, or noncompliance do not apply and the subject or parent/caregiver preferred the subject to continue treatment.
Major noncompliance with protocol	The medical monitor or investigator may request early discontinuation in the event of a major protocol deviation, lack of cooperation, or noncompliance. Noncompliance with study product is defined as missed doses for > 7 consecutive days (except for management of intercurrent illness) or missed doses for ≥ 3 consecutive days on 3 occasions, unless the dose was withheld for an adverse event or study product dispensing error (Section 8.7.5).
Dropout	
Parent/caregiver or subject decision	Active discontinuation choice by the parent/caregiver or subject. Subjects may permanently discontinue study treatment anytime for any reason. Do not select this category if any other category applies.
Sponsor-Initiated	
Sponsor discontinuation of study	The sponsor reserves the right to terminate the study anytime for any reason as described in Section 13.6 . The sponsor will end this study following completion of the study objectives, or earlier if deemed necessary.
Loss to Follow-Up	
Loss to follow-up	Cessation of subject participation without notice or action. Loss to follow-up procedures are described in Section 5.6 .

IV, intravenous.

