Up-dosing will be approximately 6 months (22-40 weeks), with dose escalation occurring approximately every 2 weeks. Daily doses of study product during up-dosing will be 1, 3, 6, 12, 20, 40, 80, 120, 160, 200, 240, and 300 mg/day. The first dose of study product at each new dose level will be administered under medical supervision at the study site; the remaining doses at each dose level will be administered daily at home as tolerated. Dose adjustments may be allowed. Subjects who reach the 300 mg/day dose within 40 weeks and tolerate the first 300 mg dose with no more than mild symptoms that are not dose-limiting will begin the maintenance period. Subjects who do not reach the 300 mg/day dose within 40 weeks of day 1 will discontinue early from the study.

Subjects who begin maintenance treatment will continue daily dosing with study product at 300 mg/day for approximately 12 weeks, which may be extended by up to an additional 4 weeks to accommodate dose adjustments during the last 2 weeks of maintenance. Study site visits will occur approximately every 4 weeks. Study product will be administered under medical supervision at the study site during maintenance visits; subsequent maintenance doses will be administered daily at home as tolerated. At the end of maintenance, subjects will have an exit DBPCFC up to a single highest challenge dose of 2000 mg dried egg white protein (4043 mg cumulative) or placebo, followed by an open baked whole egg food challenge within 14 days after the second day of the exit DBPCFC. Subjects must tolerate the 300 mg daily dose of study product for approximately 2 consecutive weeks before having the exit DBPCFC.

Subjects who complete the exit DBPCFC and attempt the open baked whole egg food challenge will exit (complete) the study. Study treatment assignment will be unblinded for a subject after study exit and after all major data queries for the subject are resolved. For a subject who discontinues early from the study, study treatment assignment will be unblinded after the study is completed. Eligible subjects will have the option to enroll in an open-label, follow-on study to receive AR201 treatment until it becomes commercially available or product development is terminated.

At early discontinuation or study exit, subjects with unresolved adverse events or who had gastrointestinal (GI) adverse events of interest (ie, GI adverse events that result in dose

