3.5 Duration of Study

The total duration of treatment is approximately 9 months for each subject.

The total duration of the study is approximately 22 months.

The end of the study is defined as the last assessment for the last subject in the study.

The total duration of the study and duration of study treatment for individual subjects may be affected by a pandemic, epidemic, or other emergency not related to the study as described in [Appendix 3](#).

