10.2 Analysis Populations

The intent-to-treat (ITT) population (ie, full analysis set) will be defined as all subjects who receive any part of one dose of study product. The ITT population will be used for all efficacy analyses unless otherwise specified, and analyzed according to randomized treatment. If no subjects receive the incorrect treatment, the ITT population will be the same as the safety population.

The completer population will be defined as all subjects in the ITT population who complete study treatment and have an evaluable exit DBPCFC (completion of at least the dried egg white food challenge day).

The per protocol population may be defined if it is sufficiently different from the completer population. The per protocol population will include all subjects in the completer population who have no major protocol deviations.

The safety population will be defined as all subjects who receive any randomized study treatment (ie, who receive any part of one dose of study product and complete one study visit). The safety population will be used for all safety analyses and analyzed according to treatment received.

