10.6 Analysis of Safety

All safety analyses will be performed using the safety population. Safety data will be summarized and listed by treatment received.

Safety data will be collected from signed informed consent and assent (where required) through 14 days after the last dose of study product, or through study exit for subjects receiving AR201 treatment in a follow-on study.

Adverse events will be classified by system organ class and coded to preferred term using the Medical Dictionary for Regulatory Activities (MedDRA). Adverse events will be classified by severity using the systemic allergic reaction grading system for systemic allergic reactions including anaphylaxis, and the general adverse events grading system for all other adverse events ([Section 8.6](#)). Anaphylaxis is defined as a severe, potentially life-threatening systemic allergic reaction (ie, grade ≥ 3 per the systemic allergic reaction grading system [[Section 8.6](#)]) that meets the criteria for anaphylaxis per [Section 8.4.1](#).

Summaries of the safety of AR201 and placebo treatment during the study will include the following:

- Overall summary of adverse events
- Incidence of all nonserious and serious adverse events
- Incidence of adverse events by severity grade
- Incidence and severity of treatment-related adverse events
- Incidence of dose modifications
- Exposure-adjusted event rates for the most frequent adverse events (ie, adverse events in $\geq 5\%$ of the safety population)
- Exposure-adjusted event rates for the most frequent treatment-related adverse events (ie, adverse events in $\geq 5\%$ of the safety population)
- Incidence of early treatment discontinuation due to adverse events and due to chronic or recurrent GI adverse events
- Separate summaries will be presented for adverse events considered allergic reactions, systemic allergic reactions, use of epinephrine, and accidental/nonaccidental food allergen exposure

Adverse events with onset before the first dose of study treatment will be listed only.

All medications will be coded using the World Health Organization Drug Dictionary (WHO-DD). Medications will be listed and summarized by Anatomical Therapeutic Chemical (ATC) classification system level 1 and preferred name.

- Prior and concomitant medications, excluding rescue medications, will be summarized separately by ATC class, preferred name, and treatment.

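### Section 5.3 defines early treatment discontinuation by about 9 months of treatment with a 4-week floor at 300 mg/day, which fits neither the planned course nor the protocol's own rules for adverse-event stops in maintenance

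*Protocol*

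**What the plan says.** Section 5.3 of the protocol defines early treatment discontinuation as a permanent stop of study product "anytime before completing approximately 9 months of overall treatment (initial dose escalation, up-dosing, and maintenance), including at least 4 weeks at 300 mg/day". Subjects in that class have early-discontinuation procedures about 14 days after the last dose.

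The planned course is set elsewhere:

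- Section 3.5: "The total duration of treatment is approximately 9 months for each subject".
- Section 5.2.3.2, on up-dosing: "minimum 22 weeks if up-dosing proceeds without holding or reducing a dose level; maximum 40 weeks".
- Section 3.1: subjects who enter maintenance "will continue daily dosing with study product at 300 mg/day for approximately 12 weeks".
- Section 5.2.3.3: "Maintenance visits will occur every 4 weeks for approximately 12 weeks". It adds: "The maintenance period may be extended by up to an additional 4 weeks", to allow for dose adjustments near the end. The exit DBPCFC comes at the end of maintenance.

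The term is used in the safety analysis. Section 10.6 lists "Incidence of early treatment discontinuation due to adverse events and due to chronic or recurrent GI adverse events". In Section 10.2, completers must "complete study treatment and have an evaluable exit DBPCFC".

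Three places treat an adverse-event stop as early discontinuation without a week limit. They are the general adverse-event rows of Table 4 (Section 5.3), Table 13 (Section 8.7.3.2, covering up-dosing and maintenance) and Section 8.7.6.4, which foresees early discontinuation for severe symptoms in maintenance. The combination of 9 months and 4 weeks at 300 mg/day appears again only in Section 13.6. There it decides who may still have the exit challenge if the sponsor closes the study.

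**The concern.** Up-dosing time varies by 18 weeks between subjects (40 − 22), so one calendar total cannot mark the end of treatment for all of them. For a slow up-doser the 9-month condition is met early in maintenance, or before it starts. The 4-week floor then becomes the only remaining test. A permanent stop later in maintenance is not early by the definition, although Tables 4 and 13 call it early.

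The discontinuation summary in Section 10.6 is at stake. Tolerability is a secondary objective (Section 2.2) of a first-in-human study (Section 1.2). The same stop could be classified differently by two sites or two programmers, depending on which passage they follow. Some procedures also depend on the term: the 14-day visit in Section 5.3, and the monthly site visits in Section 5.5.1 for subjects who stop early because of GI events.

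**Working it through.** **Inputs.** Up-dosing of 22 to 40 weeks (5.2.3.2); maintenance of about 12 weeks, extendable by up to 4 (5.2.3.3); definition threshold of about 9 months with at least 4 weeks at 300 mg/day (5.3). Let U be the week, counted from day 1, in which 300 mg is reached. A month is 52.18/12 = 4.35 weeks, so 9 months is 39.1 weeks. I use 39, with 36 as a sensitivity value because the text says approximately.

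**The plan's own figure.** About 6 months of up-dosing (26 weeks) plus 12 weeks of maintenance is 38 weeks, and 38/4.35 = 8.7 months. The stated 9 months is therefore right for a typical course. The extremes are 22 + 12 = 34 weeks (7.8 months) and 40 + 12 = 52 weeks (12.0 months).

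**Formula.** With M the 9-month value in weeks:

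- a stop is no longer early from week T = max(M, U + 4);
- planned treatment ends at week E = U + 12;
- the uncovered window is E − T. A negative value means that a subject who completed all maintenance still falls short of the threshold.

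| U (weeks) | E | T (M=39) | E − T (M=39) | T (M=36) | E − T (M=36) |
|---|---|---|---|---|---|
| 22 | 34 | 39 | −5 | 36 | −2 |
| 24 | 36 | 39 | −3 | 36 | 0 |
| 27 | 39 | 39 | 0 | 36 | 3 |
| 30 | 42 | 39 | 3 | 36 | 6 |
| 32 | 44 | 39 | 5 | 36 | 8 |
| 35 | 47 | 39 | 8 | 39 | 8 |
| 40 | 52 | 44 | 8 | 44 | 8 |

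The window cannot exceed 12 − 4 = 8 weeks without an extension. A 4-week extension moves E to U + 16 and adds up to 4 weeks, for a maximum of 12. Stops in the first 4 weeks at 300 mg/day are always early.

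**Two subjects at the same point of maintenance (M=39).** Each stops for an adverse event after 5 weeks at 300 mg/day.

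- U=36, stop at week 41: T = max(39, 40) = 40, so the stop is not early.
- U=22, stop at week 27: T = max(39, 26) = 39, so the stop is early.

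The classification differs only because of up-dosing speed. Under Tables 4 and 13 both are early discontinuations if the event requires dosing to stop.

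**The case against.** The strongest reply is that the 39-week cut-off reads too much into a loose sentence. Section 5.3 names all three treatment periods, and Section 3.5 uses about 9 months as the label for the whole course. A strict cut-off would class the 22-week up-doser who finishes at week 34 as early, which nobody intends. This has force. It also shows that the sentence gives no usable boundary: it works at either end of the up-dosing range only if approximately is stretched by several weeks.

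A reader might infer that the definition rests on 4 weeks at 300 mg/day alone. It does not. The 9-month condition applies as well, and the 4-week floor is the deciding test only when U is about 35 or more (32 or more if 9 months is read as 36 weeks).

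A reader might also infer that these stops go unrecorded. They do not. Section 8.8 requires any adverse event that leads to permanent treatment discontinuation to be entered on a case report form, and sites following Table 4 or Table 13 would call the stop early. GI safety follow-up has a second trigger in Section 8.7.6.2.1, withholding product for more than 7 consecutive days, which a permanent GI stop also meets. What could differ is the class used in the Section 10.6 summary and the monthly visit schedule of Section 5.5.1.

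Tabulation details are deferred to the SAP. That does not remove a conflict inside the protocol's own definition.

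**Conclusion.** The point holds as a conflict between a stated definition and the rest of the protocol. By the wording of Section 5.3, and with 9 months taken as 39 weeks, permanent stops in up to 8 of 12 maintenance weeks are not early for subjects with U from 35 to 40. The window is smaller for U between 27 and 35. A full completer with U=22 falls 5 weeks short of the threshold. The incidence of early discontinuation due to adverse events could be undercounted, or classified inconsistently, among slow up-dosers.

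The number of subjects affected cannot be computed, because the protocol gives no distribution of up-dosing time. Two stronger conclusions are tempting and are not supported:

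- **That AR201 would look better tolerated than it is.** Section 1.1 cites a US trial with adverse events after 25.0% of active doses and 3.9% of placebo doses, so slower up-dosing on AR201 is plausible. Delays also arise from intercurrent illness, atopic flares and menses (8.7.4), missed doses (8.7.5) and pandemic restrictions (Appendix 3). No imbalance between arms can be shown.
- **That subjects who stop after 4 weeks of maintenance enter the completer population.** Section 10.2 also requires an evaluable exit DBPCFC. Section 5.2.3.3 asks for about 2 consecutive weeks of tolerating 300 mg/day first, with an exception only for reasons unrelated to study product. A subject who stopped for a product-related event would not normally qualify.

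The primary endpoint is little affected, because a subject without a tolerated exit dose of at least 1000 mg is a nonresponder (10.5.1). Sample size and power do not change.

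**What to change.** Reconcile Section 5.3 with Sections 3.1 and 5.2.3.3, Table 4, Table 13 and Section 8.7.6.4. For classification and reporting only, define early treatment discontinuation as a permanent stop of study product before the end of the subject's planned maintenance period, including any permitted extension. Keep the 9-month/4-week clause only in Section 13.6, for sponsor closure. Use the same definition for the Section 10.6 summary and for completion of study treatment in Section 10.2.

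The uncovered window then becomes 0 weeks for every U, and a 22-week up-doser who finishes maintenance is no longer at risk of being called early. No dosing or stopping rule changes. The sponsor should state whether the visit and follow-up triggers in Sections 5.3 and 5.5.1 use the same definition.

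The cost is one definition sentence and two cross-references. The reported discontinuation rate may be slightly less favourable.
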